## **7.2 Reporting Procedures for All Adverse Events**

The investigator is responsible for ensuring that all adverse events (as defined in Section 7.1) observed by the investigator or reported by subjects after the first dose of each subject are properly captured in the subject’s medical records and reported on the eCRF.

Documentation must be supported by an entry in the subject’s file. A laboratory test abnormality considered clinically relevant, e.g., causing the subject to withdraw from the study, requiring treatment or causing apparent clinical manifestations, or judged relevant by the investigator, should be reported as an adverse event. Each event should be described in detail along with start and stop dates, severity, relationship to investigational product, action taken, and outcome

### **7.2.1 Relationship of Adverse Event to Study Drug**

The following adverse event attributes must be assigned by the investigator: adverse event diagnosis or syndrome(s) (if known, signs or symptoms if not known); event description (with detail appropriate to the event); dates of onset and resolution; severity; assessment of relatedness to study drug and action taken. The investigator may be asked to provide follow-up information, discharge summaries, and extracts from medical records or eCRFs.

If applicable, the relationship of the adverse event to the study drug will be assessed by means of the question: “Is there a reasonable possibility that the event may have been caused by the study drug?” The investigator should respond to this question with either Yes or No.

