### **3.5 Treatment**

#### **3.5.1 Treatment to be Administered**

At Visit 2 (Week -5), a subject, who is qualified for this study, will be randomized to one of two study groups and the adipose tissue will be harvested via liposuction. At Visit 3 (Week 0, baseline), the randomized subject will receive a single intra-articular injection.

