### 4.2 Treatment Period

#### **4.2.1 Visit 2 (Week -5)**

For subjects who are preliminarily eligible for this study based on screening procedures, Visit 2 will occur within approximately 2 weeks ( $\pm$  4 days) after Visit 1. During this visit, the following assessments/procedures should be performed:

[figure not shown]
- Measure vital signs (sitting blood pressure, pulse, breathing, and temperature) and weight.
- Confirm medical and medication history.
- Determine the final eligibility.
- Randomize to one of two groups (Please follow the randomization instruction separately provided by the sponsor).

Subjects who are finally eligible will then be taken to the operation room for the procedure of liposuction.

- In sterile conditions, approximately 10 – 40 mL of fat will be harvested using the syringe liposuction technique with Tumescent (or super-wet) local anesthesia (Please follow the liposuction instruction separately provided by the sponsor).
- Ship the packaging box containing the harvested syringe to Biostar SCRI designated by the sponsor (pre-labeled).
- Dispense a concomitant medication note.

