#### 4.2.3 Visit 3 (Week 0)

Visit 3 will occur within 5 weeks after Visit 2. During this visit, the following assessments/procedures should be performed:

- The following questionnaires/procedures will be completed: WOMAC (see Appendix 3), VAS (see Appendix 4), Lysholm scale (see Appendix 5), KOOS (see Appendix 6), IKDC (see Appendix 7), and RAND-36 (see Appendix 8).
- Measure vital signs (sitting blood pressure, pulse, breathing, and temperature) and weight.
- Record any adverse event and any change in concomitant medications.

- Perform a complete physical examination.
- Measure 12-lead ECG.
- Collect blood and urine samples for hematology, serum chemistry, and urinalysis.
- Inject the final drug product into the cavity of knee joint (Please follow the intra-articular injection instruction separately provided by the sponsor).
- Dispense a concomitant medication note.

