## **6.2 Determination of Sample Size**

There was no formal sample size calculation since this is a proof-of-concept study and is not a hypothesis-driven study. The number of enrolled subjects is predefined at n=30, for 20 subjects per study group and 10 subjects per control group.

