### **7.2.2 Adverse Event Severity**

The severity of adverse events should be graded as follows:

- Mild – Usually transient in nature and generally not interfering with normal activities
- Moderate – Sufficiently discomforting to interfere with normal activities
- Severe – Prevents normal activities

Medically significant adverse events considered related to the study drug by the investigator or Sponsor will be followed until resolved or considered stable.

It will be left to the investigator’s clinical judgment to determine whether an adverse event is related and of sufficient severity to require the subject’s removal from treatment or from the study. A subject may also voluntarily withdraw from treatment due to what he or she perceives as an intolerable adverse event. If either of these situations arises, the subject should be strongly encouraged to undergo an end-of-study assessment and be under medical supervision until symptoms cease or the condition becomes stable.

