7.1 ADVERSE EVENTS

AEs will be coded by SOC and PT using the MedDRA (Version 18.1). The verbatim term will be included in the AE listing.

A treatment-emergent adverse event (TEAE) is defined as an AE that occur or worsen on or after the injection of study drug and before the end of the study. Only TEAEs will be included in summary tables. All AEs, treatment emergent or otherwise, will be presented in subject data listings.

The TEAEs will be summarized as the number (percentage) of subjects with TEAEs within SOC and PT. Subjects who report the same PT on multiple occasions will be counted once for the PT: under the highest severity (severe > moderate > mild) when summarized by severity and under the closest relationship to study drug when summarized by relationship. If a subject reports multiple PT for a SOC, the subject will be counted only once for that SOC.

TEAEs will be summarized as below.

- An overview table, including number of subjects with
 - TEAEs
 - serious AEs (SAEs)
 - study drug related TEAEs
 - TEAEs by severity
 - TEAEs leading to study discontinuation
 - TEAEs leading to death
- TEAE by SOC and PT
- TEAE by SOC, PT, and Severity
- Study drug related TEAEs by SOC, PT
- SAEs by SOC and PT
- TEAEs leading to study discontinuation by SOC and PT

All AE tables will be sorted by SOC and PT in decreasing frequency of the number and percentage of subjects summarized by treatment group and total.

Missing date will be imputed followed table describes how missing date information will be handled:

| Partial Missing Start or Stop Date | Imputed Start Date | Imputed Stop Date |
|--|--|-----------------------------------|
| Missing month and day, and the year is present | January 1 of that year or first dose date if the year is the same as the year of first dose date | December 31 of that year |
| Missing day, but year and month are present | First day of that month or first dose date if the year and month are the same as the year and month of first dose date | Last day of that month |
| Missing month, but year and day are present | Missing month imputed as January | Missing month imputed as December |

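### Adverse event causality is recorded only against the study drug, so harms of the liposuction that JointStem requires are not reliably attributed to the regimen, and the comparison of arms cannot be expected to show them

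*Protocol*

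**What the plan says.** **Causality.** Protocol 7.2.1 poses one question, "Is there a reasonable possibility that the event may have been caused by the study drug", answered Yes or No. Section 7.2 lists what is described for each event, including "severity, relationship to investigational product, action taken, and outcome". Protocol 6.1.6 breaks event rates down by relation to study drug, and SAP 7.1 plans a table of "Study drug related TEAEs by SOC, PT". No question, field or table in either document concerns relation to a study procedure.

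**Exposure.** Under protocol 3.5.1 a qualified subject "will be randomized to one of two study groups and the adipose tissue will be harvested via liposuction" at Visit 2. Section 4.2.1 adds: "Subjects who are finally eligible will then be taken to the operation room for the procedure of liposuction". This applies to both arms. On the interval to injection, 4.2.3 says: "Visit 3 will occur within 5 weeks after Visit 2". The planned split is 20 JointStem and 10 control (6.2). The control syringe is purchased (3.5.2), so only JointStem needs the fat.

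**Follow-up.** Protocol 7.2.2: "Medically significant adverse events considered related to the study drug by the investigator or Sponsor will be followed until resolved or considered stable". Two other duties carry no causality condition: section 7.3 on following serious events, and section 3.3 on keeping contact with subjects removed because of an adverse event.

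**Time windows.** Section 7.2 captures events after the first dose, and 7.3 collects serious events from drug administration. Section 3.6.3 collects events at all visits after randomization, which takes place at Visit 2. The Visit 3 list in 4.2.3 has an adverse event item. The safety population is defined by completing Visit 2 (protocol 6.1.1.3, SAP 2.2.3). SAP 7.1 tabulates only events that begin or worsen on or after injection; the rest go to listings.

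**The concern.** The safety objective concerns a treatment that cannot be given without a surgical harvest. There are two ways to see the harm of one component of a regimen: attribute events to it, or compare subjects who had it with subjects who did not. The second is closed because both arms have liposuction. The first depends on a question that names only the study drug. An investigator who reads it literally would answer No for a harvest-site event, and that answer then governs both the related-event table and the general follow-up sentence. A reader of the final tables could take the drug-related rate as the burden of receiving JointStem, when the harvest part of that burden is missing from it.

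**Working it through.** The plan states no figure on this point, so the check follows a procedure-caused event through capture, causality, follow-up and tabulation.

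1. **Harvest event, starts before injection, does not worsen.** Outside the capture window in 7.2, but inside that of 3.6.3 and recordable at Visit 3. It is not treatment-emergent under SAP 7.1, so it appears in listings only, whatever the causality answer. If serious, it precedes the collection start in 7.3.
2. **Harvest event that begins or worsens on or after injection.** Treatment-emergent, so it enters the overall tables. It enters the related table only if the study-drug question is answered Yes.
3. **Event caused by the joint puncture.** Same route as 2. Here the causality wording alone decides the classification, and Yes is plausible.
4. **Serious event within the 7.3 window, or event leading to removal.** Followed whatever the causality answer (7.3, 3.3).
5. **Non-serious, medically significant event, answered No, subject stays in.** Not covered by 7.2.2, 7.3 or 3.3 as a duty to follow to resolution.

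**What each repair does alone.** Adding a procedure question leaves route 1 in listings. Widening the window brings route 1 into the tables, but with nothing to mark those events as procedure-related. Both changes are needed.

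**Size, by assumption only.** Let q be the share of subjects with a liposuction-caused event, the same in both arms, and take q from 5% to 30%:

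- JointStem: 20 × 0.05 = 1 to 20 × 0.30 = 6 subjects
- Control: 10 × 0.05 = 0.5 to 10 × 0.30 = 3 subjects
- Expected between-arm difference: q − q = 0 for every q

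If all such events were answered No, and none of these subjects had another related event, the related share would omit up to q. That upper bound combines routes 1 and 2. The documents give no basis for splitting it between the treatment-emergent rule and the causality wording.

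**The case against.** The other side has good points, and they limit the claim.

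- A reader might infer that liposuction harms as a class go unfollowed. The documents do not support that. Serious events within the collection window and subjects removed for an event are followed regardless of causality, and 7.2 asks for stop dates and outcome on every event. What remains is route 5. Serious events before injection are missed because of the start date in 7.3, not the causality question.
- A reader might infer that the causality wording is what keeps harvest events out of the tables. For events that start before injection and do not worsen, the treatment-emergent definition does that on its own.
- A reader might infer that procedure events can never be called related. Study drug is not defined so as to exclude its delivery, and the event definition in 7.1.1 covers any route of administration, so Yes for a joint event after injection is defensible. But nothing directs investigators either way, and two or three centers may answer differently.
- A reader might infer that the study-discontinuation criteria in 3.4 depend on the same answer. They do not: the serious-event criterion there uses a different threshold and refers to administration of the drug, and other criteria, such as the death count, need no relatedness.
- Giving both arms liposuction is part of a double-blind design and is not an analysis error. A causality field will not make the expected difference anything but zero. That is why attribution has to carry the information.
- The listings with verbatim terms, and the total column, would let someone find harvest-site events by hand. That is not a planned summary.
- The eCRF is not among the documents, and it may already hold such a field. If so, the protocol and SAP still do not use it.

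**Conclusion.** The concern holds in limited form. Attribution is recorded only against the study drug, and the design removes the between-arm contrast, so neither route reliably shows harvest harm. The general follow-up sentence does not clearly reach non-serious, medically significant procedure events in subjects who remain in the study. Pre-injection harvest events that do not worsen are absent from all tables for a separate reason, the treatment-emergent definition. The collection start dates in 7.2 and 7.3 are at odds with 3.6.3 and with the safety population definition.

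The direction, a related-event table that tends to understate the burden of the regimen, does not depend on the assumed rate. Its size does, and the 5% to 30% range has no source in the documents. The conclusion also assumes that investigators read study drug as the injected product. Efficacy analyses and sample size are unaffected. The change should be made because safety is half of the stated objective.

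**What to change.** - **Protocol 7.2.1:** add a Yes/No question on relation to a study procedure, with liposuction and intra-articular injection recorded separately. Match the attribute list in 7.2.
- **Protocol 7.2.2, 3.3 and 7.3:** reconcile these so that it is clear which events are followed, and state whether procedure-related events are among them.
- **Protocol 3.6.3, 7.2 and 7.3:** set one collection start for adverse and serious adverse events that includes Visit 2, consistent with the safety population.
- **SAP 7.1:** add a table of all events from Visit 2 in the safety population, with drug-related, procedure-related and combined counts, by arm and in total. Count each subject once in the combined figure. The treatment-emergent tables can stay alongside.

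**Cost:** an eCRF item (one field, or one for each procedure), protocol wording and extra table columns. Reported related-event rates may rise, and the report should explain that this reflects wider attribution.

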### **7.2.2 Adverse Event Severity**

The severity of adverse events should be graded as follows:

- Mild – Usually transient in nature and generally not interfering with normal activities
- Moderate – Sufficiently discomforting to interfere with normal activities
- Severe – Prevents normal activities

Medically significant adverse events considered related to the study drug by the investigator or Sponsor will be followed until resolved or considered stable.

It will be left to the investigator’s clinical judgment to determine whether an adverse event is related and of sufficient severity to require the subject’s removal from treatment or from the study. A subject may also voluntarily withdraw from treatment due to what he or she perceives as an intolerable adverse event. If either of these situations arises, the subject should be strongly encouraged to undergo an end-of-study assessment and be under medical supervision until symptoms cease or the condition becomes stable.

## **7.3 Serious Adverse Event Reporting Procedures**

Serious adverse events will be collected and recorded from the drug administration to 3-month follow-ups.

Serious Adverse Events, including laboratory test abnormalities fulfilling the definition of serious, after the first dose, and during follow-up period must immediately (within 24 hours of the investigator’s awareness) be reported to the person/parties as detailed in the study file. A Serious Adverse Event form must also be completed within 1 day of the investigator’s awareness and

forwarded to the designated person/parties as detailed in the study file. Each Serious Adverse Event must be followed up until resolution or stabilization by submission of updated reports to the designated person/parties.

Serious adverse events also will be collected and reported within 1 working day of discovery or notification of the event if it occurs 7 days after the last dose of study drug or after the end of the study and is thought to be possibly related to study drug.

For all deaths, available autopsy reports and relevant medical reports should be faxed to Sponsor or their designee. For this reporting process, subject assessments must be made 7 days after administration of the last dose of study drug.

If a subject is permanently withdrawn from the study because of a serious adverse event, this information must be included in the initial or follow-up Serious Adverse Event Report Form as well as the End of Study Case Report Form.

When required, and according to local law and regulations, serious adverse events must be reported to the institutional review board and Regulatory Authorities.

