### Schedule of Assessments

	Screen.	Harv.	Treat.	1 st Follow-up				2 nd Follow-Up		Long-term	
Blinding	N/A	Double Blinding							Open 		Follow-up
Visit	1	2	3	4	5	6	ET	7	8	N/A	
Week / Month	W-7	W-5	0	M1	M3	M6	<M6	M9	M12 or Final FU 	M24	
Informed consent	X										
Medical and Medication History	X	X									
Demographic information	X										
Complete physical examination	X		X		X	X	X 	X	X	X	
Vital signs and weight	X	X	X	X	X	X	X	X	X	X	
Hematology, serum chemistry, and urinalysis 	X		X	X	X	X	X 	X	X		
Pregnancy test 	X					X	X 		X		
HIV test for Screening	X										
12-lead ECG	X		X			X	X 		X		
X-ray	X										
Eligibility confirmation	X	X									
Randomization		X									
Liposuction		X									
Injection of final drug product			X								
AE and concomitant medication assessment			X	X	X	X	X	X	X		
Records of Treatment and Medications										X	
MRI scan 	X					X	X 		X	X	
WOMAC			X	X	X	X	X 	X	X	X	
VAS	X		X	X	X	X	X 	X	X	X	
Lysholm			X	X	X	X	X 	X	X	X	
KOOS			X	X	X	X	X 	X	X	X	
IKDC			X	X	X	X	X 	X	X	X	
Quality of Life (RAND-36)			X		X	X	X 	X	X	X	

1. See Appendix 1 for the complete list of laboratory tests
2. Serum pregnancy test is performed for all females of childbearing potential (please refer to the relevant inclusion criteria)
3. May be performed the day of Visit 2 or after due to scheduling or re-scanning.
4. Performed only if the early termination is after V3.
5. Performed only if the early termination is after V4.
6. Performed if the follow-up is discontinued after V6.
7. Only for JointStem group.

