### **3.3 Removal of Subjects from Study**

Subjects may be withdrawn from the study for the following reasons:

- At their own request or at the request of their legally acceptable representative
- If, in the investigator's opinion, continuation in the study would be detrimental to the subject's well-being
- At the specific request of the sponsor

Also, subjects must be withdrawn for the following reasons:

- A significant violation of the protocol, as determined by the sponsor or the investigator
- Highly significant abnormalities in the laboratory results (Highly significant abnormalities generally follow lab related exclusion criteria, but a PI can determine the high significance on any abnormalities for the safety of subject)
- Use of any other investigational drugs (including placebo)
- Subjects enrolled in the current trial but taking any prohibited medication/therapy stated in the inclusion/exclusion criteria that, in the investigator's opinion, will interfere with the study outcome.
- Subject enrolled in the current trial but having a baby

If a subject prematurely withdraws from the study, the subject must return to the clinical site for the early termination visit. In all cases, the reason for withdrawal must be recorded in the electronic Case Report Form (eCRF) and in the subject's medical records.

Contact will be maintained with subjects who are removed due to an adverse event (AE) until it has been resolved or stabilized, and the information will be documented in the eCRF and in the subject's medical records.

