### **3.4 Premature Termination of Study / Closure of Center**

The sponsor has the right to terminate this study, and the investigator/sponsor has the right to close a clinical site, at any time, although this should occur only after consultation between involved

parties; the IRB must be informed in any case. Should the clinical site be closed prematurely, all study materials (equipment, study medication, etc.) must be returned to the sponsor.

This study will discontinue due to medical or administrative reasons such as:

- Serious adverse events probably related to study drug administration so that the use of study drug may no longer be justifiable
- 2 or more deaths are observed during any point in the trial
- 5 or more adverse drug reactions (NCI-CTCAE  $\geq$  Grade 3) on the injected joint are observed during any point in the trial
- Significant change of benefit-risk ratio for the subjects
- Sponsor discontinues the investigation of JointStem for the treatment of osteoarthritis or determines that the doses being studied are no longer justifiable

Possible reasons for closing of a clinical site include the following:

- The investigator feels that the number or severity of adverse events is excessive
- A change of technical, administrative, or personal circumstances occurs and the conduct of the study no longer meets ICH-GCP guidelines
- In case of evident, significant non-compliance to protocol or poor data quality

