### **3.6.3 Safety Variables**

- Hematology, serum chemistry and urinalysis at Visits 1, 3, 4, 5, 6, 7 and 8 (Screening, Baseline, M1, M3, M6, M9 and M12) or Early Termination (only if the subject is early terminated after Visit 3) or Final Follow-up Visit. See Section Appendix 1 for a complete list of laboratory tests to be done.
- ECG evaluation at Visits 1, 3, 6 and 8 (Screening, Baseline, M6 and M12) or Early Termination (only if the subject is early terminated after Visit 3) or Final Follow-up Up Visit
- Complete physical examination at Visits 1, 3, 5, 6, 7 and 8 (Screening, Baseline, M3, M6, M9 and M12) or Early Termination (only if the subject is early terminated after Visit 3) or Final Follow-up Up Visit
- Vital signs (sitting blood pressure, pulse, breathing, and temperature) and weight will be measured at all visits.
- Data regarding AEs and concomitant medications collected at all visits after randomization

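### Adverse-event reporting, SAE collection and the 24-hour SAE duty start at injection, although every randomized subject has liposuction up to five weeks earlier

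*Protocol*

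**What the plan says.** Protocol Section 3.5.1 puts randomization and fat harvest at Visit 2 (Week -5) and one intra-articular injection at Visit 3 (Week 0). Section 4.2.1 makes no distinction by arm: "Subjects who are finally eligible will then be taken to the operation room for the procedure of liposuction". Section 4.2.3 allows up to five weeks between the two visits.

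The reporting rules are tied to the injection:

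- Section 7.2 makes the investigator responsible for capturing adverse events "observed by the investigator or reported by subjects after the first dose of each subject".
- Section 7.3 opens: "Serious adverse events will be collected and recorded from the drug administration to 3-month follow-ups".
- Section 7.3 then sets the expedited duty: "Serious Adverse Events, including laboratory test abnormalities fulfilling the definition of serious, after the first dose, and during follow-up period must immediately" be reported to the designated parties. The limit is 24 hours from the investigator's awareness.

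Other text reaches further back. Section 3.6.3 lists "Data regarding AEs and concomitant medications collected at all visits after randomization". In the Schedule of Assessments (repeated in SAP Table 1), the row "AE and concomitant medication assessment" is empty at Visit 2, is marked from Visit 3 onward, and is marked at early termination without the footnote that restricts other items to terminations after Visit 3. Section 3.3 adds: "If a subject prematurely withdraws from the study, the subject must return to the clinical site for the early termination visit".

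The Safety population (Protocol 6.1.1.3, SAP 2.2.3) starts at randomization plus completion of Visit 2. SAP 7.1 defines a treatment-emergent event as one that occurs or worsens at or after injection. It restricts summary tables to those events and lists everything else.

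**The concern.** Liposuction under local anesthesia is required by the protocol in both arms, including controls whose product is a purchased hyaluronic acid syringe. The protocol itself treats it as carrying risk: exclusions 11, 13 and 15 screen for liposuction problems, local anesthetic allergy, and unsafe interruption of aspirin or Plavix before Visit 2. If that risk materializes, however, the expedited-reporting rule has not yet begun.

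Sites follow Section 7.3 when they decide what to send to the sponsor. A site following it as written could learn of a serious wound, bleeding or anesthetic complication after Visit 2 and owe no 24-hour report, while other subjects go on to the same procedure. SAP 8.2 plans no DSMB, so the sponsor's discretionary power to stop under Section 3.4, including the ground "Significant change of benefit-risk ratio for the subjects", depends on what sites report.

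There is also a reporting consequence. Subjects enter the safety denominator at Visit 2, but harms from the procedure that put them there are tabulated only if they worsen after injection.

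**Working it through.** No power or alpha calculation applies. The check sets the rules side by side.

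**Inputs**
- First dose: the only dose is the Visit 3 injection (Protocol 3.5.1).
- Harvest: Visit 2, both arms (3.5.1, 4.2.1).
- Maximum interval: 5 weeks × 7 = 35 days (4.2.3).
- Planned subjects: 20 + 10 = 30 (6.2).

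**What the documents require for an event, by when it occurs**

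| Situation | Recorded in the data? | 24-hour report if serious? | In SAP tables? |
|---|---|---|---|
| After harvest, subject later injected | Yes, at Visit 3; recording is listed before the injection step (4.2.3) | No duty stated | Only if it worsens on or after injection |
| After harvest, subject never injected | At early termination (3.3, 4.2.9, Schedule) | No duty ever starts | No; listings only |
| On or after injection | Yes | Yes, under 7.3 | Yes |

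**Is the second row a real case?** Yes. Section 4.1 and Schedule footnote 3 allow the screening MRI on the day of Visit 2 or later, provided the result is confirmed before injection. Exclusion 25 removes subjects whose MRI shows no cartilage damage. A subject can therefore be harvested and then found ineligible.

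**Does other text in 7.1 to 7.3 fill the gap?**
- Section 7.1.1 promises ongoing review of adverse events but names no deadline or recipient. It also defines an adverse event by association with drug use, so a site could doubt that a pre-injection surgical event qualifies.
- The late-event clause in 7.3 is keyed to the last dose or the end of the study and to a possible relation to study drug.
- The sentence in 7.3 on the IRB and regulators applies where local law requires it. It sets no clock for reporting to the sponsor.

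**Does 3.6.3 contradict the rest?** Randomization is itself a Visit 2 step, performed before liposuction, so the first visit after it is Visit 3. Section 3.6.3 is therefore consistent with a Schedule that starts adverse-event assessment at Visit 3. It does conflict with 7.2, because an event reported at Visit 3 before injection is inside 3.6.3 and outside 7.2.

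**The case against.** The strongest reply is that harvest events are not lost. Visit 3 records them before injection. The early termination cell for adverse events carries no restriction to subjects past Visit 3. Section 3.3 requires contact to continue with anyone removed for an adverse event until it resolves or stabilizes. SAP 7.1.1 lists serious events, discontinuations and deaths without limiting them to treatment-emergent ones. The stopping rule on two or more deaths in Section 3.4 applies at any point in the trial. With about 30 subjects, a listing discloses a great deal.

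All of this stands, and it rules out several stronger readings that a reader might infer:

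- *No pre-injection event is ever collected.* The Visit 3 and early termination procedures show otherwise.
- *Section 3.6.3 contradicts the blank Visit 2 cell.* It does not; its conflict is with 7.2 alone.
- *The sponsor hears after 35 days instead of one.* The two are not comparable: 35 days is the longest wait for a scheduled visit, whereas the 24 hours run from the investigator's awareness.
- *Subjects multiplied by days measures the harm.* Without an event rate, that product measures no risk.
- *The SAP hides harvest harm.* Events that worsen after injection are tabulated, and the rest are listed.

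What the reply does not supply is a duty to send a known serious harvest event to the sponsor promptly. Scheduled data capture and end-of-study listings serve a different purpose. The sponsor's separate liposuction instruction and the study file might contain such a rule. They are not among the documents reviewed, and any such rule would still sit beside a Section 7.3 that begins at dosing.

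**Conclusion.** The point holds for reporting duties and, to a lesser degree, for tabulation. Sections 7.2 and 7.3 leave up to 35 days after a mandated procedure outside adverse-event reporting, SAE collection and the 24-hour rule, for all 30 planned subjects. For anyone harvested but not injected, those duties never begin. The 35 days is a maximum, since Visit 3 may come sooner.

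The documents give no rate of serious harvest complications, so no expected number of affected reports can be given. The conclusion assumes that the first dose means the Visit 3 injection, the only dose in the protocol, and that no unseen instruction supplies the missing duty. The efficacy analyses are unaffected. The amendment should be made because the rule as written gives a worse safety result when followed exactly, and the change is small.

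**What to change.** 1. In Protocol 7.2 and 7.3, move the start point for adverse-event recording, SAE collection and 24-hour reporting from the first dose or drug administration to the start of liposuction at Visit 2.
2. In 7.1.1, state that events associated with the tissue harvest count as adverse events.
3. In 4.2.1, add adverse-event recording after the liposuction step, and mark the Visit 2 cell of that row in the Protocol Schedule and SAP Table 1.
4. In SAP 7.1, keep the treatment-emergent definition and add one summary of adverse events from the start of liposuction to injection, in the Safety population.
5. Leave the Section 3.4 criteria as they are.

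The cost is a wording amendment, one Schedule cell in each document, one small table and possibly some additional expedited reports. The change speeds onward reporting of events the investigator already knows about. It adds no contact between Visits 2 and 3, so a complication that the subject does not report would still first surface at Visit 3.
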